9.3 Safety Assessments

Adverse Events

Definition of an Adverse Event

The FDA Safety Guidance, referencing 21CFR312.32(a), defines an Adverse Event as follows:

Adverse event means any untoward medical occurrence associated with the use of a drug in humans, whether or not considered drug related.

An adverse event (also referred to as an adverse experience) can be any unfavorable and unintended sign (e.g., an abnormal laboratory finding), symptom, or disease temporally associated with the use of a drug and does not imply any judgment about causality. An adverse event can arise with any use of the drug (e.g., off-label use, use in combination with another drug) and with any route of administration, formulation, or dose, including an overdose.

Evaluating and Reporting of Adverse Events

All AEs will be promptly documented on the Adverse Event in RedCap and assessed by the Principal Investigator. Details of the event must include the dates of onset and resolution, severity, relationship to study drug, seriousness, and whether the event caused the subject to withdraw from the study, outcome and timing with regard to administration of the study drug.

Severity: Severity should be graded and recorded as follows:

- Mild: Awareness of event but easily tolerated
- Moderate: Discomfort enough to cause interference with usual activity

- **Severe:** Inability to carry out usual activity, incapacitating, requires medical intervention

Relationship: The relationship of the Adverse Event to the study device will be determined initially by the Investigator, and assessed using the following definitions:

- **Related:** There is a distinct temporal relationship between the event onset and administration of the study drug. There is a known reaction to agent or chemical group or predicted by known pharmacology. The event cannot be explained by subject's clinical state or other factors.
- **Unrelated:** Evidence exists that the AE has an etiology other than the study drug (e.g., pre-existing condition, underlying disease, intercurrent illness, or concomitant medication).

Final determination of relatedness will be made by the Stanford Institutional Review Board during an unanticipated problem or adverse event submission.

Expectedness: Whether or not the event was expected or unexpected. Further details on this can be found in section 8.5.

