These criteria, in addition to good clinical judgment, should be used as a guide for determining the causal assessment. If it is felt that the event is not related to study therapy, then an alternative explanation should be provided.

Serious Adverse Events (SAEs)

Suspected Unexpected Serious Adverse Reactions (SUSARs)

A SUSAR carries specific and time-based reporting requirements for the Sponsor of a clinical trial. Thus, after a Site Investigator reports an SAE, the FDA expects the Sponsor will determine whether it meets the definition of a SUSAR.

A SUSAR is defined according to 3 criteria:

1. The AE is deemed a “suspected adverse reaction” if there is a reasonable possibility that the study drug caused the AE. A “reasonable possibility” means there is evidence to suggest a causal relationship between the drug and adverse event.
2. The AE is “Serious” if it meets the definition of an SAE.
3. The AE is deemed “unexpected” if it is not listed in the Investigator’s Brochure (IB) or if in the IB, has not been reported at the severity observed.

In cases where the Investigator deems a SUSAR has occurred, it must file an IND Safety Report with the FDA. FPHU will require the assistance and cooperation of the Investigator and staff to provide accurate and complete information on the subject and observed SAE so that reporting requirements to the FDA can be met.

Reporting SUSARs to the FDA: IND Safety Reports

IND safety reports are used to submit reports of SUSARs to the FDA. There are 2 types of reports:

- A “15-day report” is used when the reported SAE is a SUSAR and requires that as much information as is available to the investigator and the sponsor, be submitted to the FDA in on the appropriate form. For US trials, the appropriate form is the FDA Form 3500A also commonly known as a “MedWatch” form.
- A “7-day report” is used when the SUSAR is considered to be fatal or life-threatening.

The 7-day and 15-day timelines begin the day that the Sponsor determines the information qualifies for reporting and are counted in calendar days – not business days. Therefore, it is important that the Site investigator carefully follow the reporting requirements.

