A CONSORT diagram displaying the number of patients screened, eligible, and consented along with reasons for ineligibility will be provided. Graphical tools such as histograms, boxplots, and scatterplots will be created to assess quality of data and to display patterns over time.

Safety Analysis

Treatment related adverse events for GuessWhat intervention will be presented. Any adverse events occurring during any phase of the study judged by clinical sites' Primary Investigator (PI) to be related to the intervention will be recorded and presented in a table listing. The Safety population (see [analysis population details](#)) will be used for this analysis that will include randomized participants. The severity of each event will be evaluated by the PI and presented with the recorded events. If there are frequently occurring treatment related adverse events,

a frequency table will be included, to rank events from most frequent to most rare. Subjects will be included in the actual treatment group received.

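### The safety listing follows the PI's initial relatedness call although the IRB's call is final, and section 9.3 names two deciders for SUSAR status

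*Combined protocol and SAP*

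**What the plan says.** **Relatedness.** Section 9.3 requires that "All AEs will be promptly documented on the Adverse Event in RedCap and assessed by the Principal Investigator". The relationship to the device "will be determined initially by the Investigator". The section then adds: "Final determination of relatedness will be made by the Stanford Institutional Review Board". That final step takes place when an adverse event or unanticipated problem is submitted to the board.

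**Listing.** The Safety Analysis text in 10.5 says that events judged by the sites' PI "to be related to the intervention will be recorded and presented in a table listing". It does not refer to the IRB's determination.

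**SUSAR status.** Section 9.3 first says that, once a site reports a serious event, the sponsor decides whether it is a SUSAR. It ties the clocks to that decision: "The 7-day and 15-day timelines begin the day that the Sponsor determines the information qualifies for reporting". Between these two statements it says "In cases where the Investigator deems a SUSAR has occurred", and makes that the trigger for filing with the FDA. A body called FPHU also has a part in the reporting and is not defined anywhere.

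**Criteria.** An event is serious "if it meets the definition of an SAE", but the SAE heading is followed at once by the SUSAR heading. On expectedness, 9.3 says: "Further details on this can be found in section 8.5". Section 8 and the table of contents have only 8.1.

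**The concern.** Section 5.2 makes the safety of home use an objective, in children aged 3 to 12. The listing in 10.5 is the main output that would answer it. If the listing rests on a judgement that the protocol itself calls initial, the reported safety result can differ from the trial's own final determination, and the reader of the listing would not know.

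The SUSAR text raises a similar problem. If the sponsor and the investigator differ, the document does not say whose view triggers filing, and the clock is tied to only one of them. Section 7.2 reports no adverse events so far. The plan gives no expected event rate, but if events are few, how a single event is handled carries more weight.

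**Working it through.** No arithmetic applies, and the plan states no figure to reproduce. The check is to follow each decision from 9.3 into 10.5.

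**1. Relatedness: every combination of calls**

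| PI (initial) | IRB (final) | Listed under 10.5 as written? | Agrees with the final call in 9.3? |
|---|---|---|---|
| Related | Related | Yes | Yes |
| Related | Unrelated | Yes, IRB call not shown | No |
| Unrelated | Related | No | No |
| Unrelated | Unrelated | No | Yes |
| Related | No submission | Yes | No final call exists |
| Unrelated | No submission | No | No final call exists |

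Of the four combinations with an IRB call, the listing departs from the final determination in two. The third row matters most, because an event finally held to be related is missing. In the second row the event appears, but the reader cannot see that the final call went the other way.

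**2. SUSAR status: two rules side by side**

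- Rule A in 9.3: the sponsor determines status, and the 7- and 15-day clocks start on that day.
- Rule B in 9.3: the investigator deems that a SUSAR has occurred and must then file.
- If only the investigator thinks it is a SUSAR, filing is required under B but no clock has started under A.
- If only the sponsor thinks so, the clock runs under A but the filing trigger in B has not been met.

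The two rules give the same result only when both parties agree.

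**3. The three SUSAR criteria**

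| Criterion | What it rests on | Can it be applied from the text? |
|---|---|---|
| Suspected reaction | A causality standard explained in place | Yes |
| Serious | The SAE definition | No; nothing stands under that heading and no definition appears elsewhere |
| Unexpected | Listing, and severity, in an Investigator's Brochure | Yes, by default; an event not listed counts as unexpected |

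One criterion of three lacks its content. The mention of fatal or life-threatening events does not fill the gap, because it only sets when the 7-day report applies. Section 9.3 also asks for seriousness to be recorded for each adverse event, so the missing definition affects routine recording as well.

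**4. The 8.5 reference.** It belongs to the Expectedness item in the adverse-event record, not to the SUSAR criteria. It is a dead cross-reference.

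**5. Other decisions.** Severity is graded by the PI in 10.5, and 9.3 has the PI assess all events. There is no conflict there.

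**The case against.** The strongest reply is that 9.3 describes a staged hand-off on relatedness, from investigator to IRB, and that stages are not a contradiction. That is right for 9.3 on its own. What remains is that 10.5 takes the first stage and has no rule for disagreement.

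A second reply is that the SUSAR conflict has little practical effect if sponsor and investigator are the same party. The documents under review do not settle that. If they are the same, the conflict largely disappears in practice, though the wording still needs repair.

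Third, this is drug and IND text applied to an app, and the route may not apply at all. That cannot be decided from the documents. It is a reason to have the sponsor confirm the route, not a reason to leave two conflicting rules in place.

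A reader might also infer more than the text supports:

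- *That adverse-event decisions in general have no owner.* Severity has one, the PI.
- *That two of the three SUSAR criteria cannot be used.* A brochure is normally a separate document, so its absence here is not an error, and an event not listed in it is unexpected by default.
- *That a serious event has no way to be escalated.* Section 9.3 has all events documented promptly and assessed by the PI, and provides for IRB submission, which does not depend on the SAE definition. Removal from treatment under 6.3 does not depend on it either.
- *That no reporting clock exists.* Section 9.3 gives a start. It gives no numeric limit from investigator to sponsor, which is missing detail and not a contradiction.
- *That no event can be expected because 7.2 reports none.* Section 7.2 refers to testing and to hazards identified by simulated use. How expectedness is judged is for the sponsor to state.

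**Conclusion.** The point holds for two contradictions: between 9.3 and 10.5 on which relatedness decision governs the listing, and within 9.3 on who decides SUSAR status and files. In two of the four PI-IRB combinations the listing does not match the final determination, and in one of those a related event is omitted. The missing SAE definition and the dead 8.5 reference are real but lesser gaps. They would not justify a point alone and are best corrected in the same edit.

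The conclusion rests on three assumptions. Some events that the PI calls unrelated reach the IRB; 9.3 does not say which events are submitted. The SAE heading is empty in the source as well; it carries no redaction mark, but loss when the text was extracted cannot be fully excluded. Sponsor and investigator can differ in their judgement. How often any of this would occur cannot be estimated, because the plan gives no event rate.

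This is a repair to safety reporting and leaves the efficacy result untouched.

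**What to change.** 1. In the Safety Analysis part of 10.5, list an event if either the PI or the IRB judges it related. Show the PI's call in one column and, where a submission was made, the IRB's final call in another. Events that were never submitted keep the PI's call, with the IRB column marked as not submitted.
2. In 9.3, reconcile the SUSAR text so that one role decides status and files, and tie the clocks to that role's decision. Define FPHU or remove it. Which role this should be is for the sponsor.
3. In the same edit, put the SAE definition under its heading and correct or delete the reference to section 8.5.
4. Have the sponsor confirm whether the drug/IND reporting route applies to this app, and state how expectedness is judged.

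The cost is protocol wording and one extra listing column. The efficacy analysis does not change.

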10. STATISTICAL METHODS AND ANALYSIS PLAN

10.1 General Considerations

For the primary comparison, the following will be tested:

- Null hypothesis: There will be no difference between the observed change in VABS-3 Socialization scores from baseline to week 4 between treatment and control participants.
- Alternative hypothesis: We will observe a minimally clinically important increase on the VABS-3 Socialization score from baseline to week 4 in the treatment group, but not in the control group.

Hypothesis tests will be two sided and conducted at an overall alpha = 0.05 level of significance.

10.2 Sample Size Justification and Power Calculation

We will enroll up to 2,000 participants to achieve a 50% enrollment rate and 36% retention rate.

We aim to successfully retain 36% of enrolled families and have 360 parents and their child with autism aged 3-12 years old complete all study procedures (180 Treatment, 180 Control).

We will close out the study after enrolling 360 participants with completed endpoints, estimated for 90% power and 2-sided significance of .05 to detect minimal differences in VABS-III Socialization Standard Score of 3.1 points, consistent with the results of a GuessWhat feasibility study previously reported by our lab.

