1. SYNOPSIS

Title	A Lead-in Study Evaluating Efficacy of GuessWhat Mobile App Therapy for Children With Autism
Design	Randomized, Investigator-Blinded,
Objectives	Determine whether GuessWhat Dtx can improve socialization in children with ASD after 4 weeks of use.
Endpoints	Primary: Change from week 0 to week 4 in the Vineland Adaptive Behavior Scales-3 Socialization Subscale, Comprehensive Parent Report Secondary: Change from week 0 to week 4 in Parent Stress Scale, and Child Emotion Recognition Score Exploratory/Descriptive: Descriptive analysis of child/parent surveys, treatment regimen compliance, demographics, missing data, and any resulting treatment related AEs
Study Sites	Participants will recruited by Stanford via remote online recruitment.
Planned Enrollment	A minimum of 500 to a maximum of 2,000 participants will be enrolled to achieve a minimum of 360 to a maximum 900 completed participants (n=180 - 450 in each of 2 arms) evaluable
Study Population	Autistic children 3-12 years old.
Subject Entry Criteria	Inclusion Criteria (1) Parent who is at least 18 years old of child with autism. (2) Child with autism is between 3 and 12 years old at time of baseline data collection. Exclusion Criteria (1) Parent does not have an Android or iOS smartphone compatible with GuessWhat App. (2) The parent is unable to speak/read in available translations of the study app: English, Spanish, Brazilian Portuguese.
Randomization	Block randomization stratified by child sex.
Treatment Regimen (Standard dose)	App is used 3 times a week for 15 minutes for 4 weeks

Duration of Study Participation	8 weeks
Statistical Methods	Independent Samples T-Tests
Study Measurements: Efficacy, Safety	Efficacy: Change in Vineland Adaptive Behavior Scales-3 Socialization Subscale week 0 to week 4 Safety: Adverse event reporting

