3.2 Previous studies

We examined the therapeutic feasibility of GuessWhat in 72 children (75% male, average age 8 years 2 months) with autism who were asked to play the game for three 90- second sessions per day, 3 days per week, for a total of 4 weeks. The group showed significant improvements in Social Responsiveness Score-2 (SRS-2) total (3.97, $p < .001$) and Vineland Adaptive Behavior Scales-II (VABS-II) socialization standard (5.27, $p=0.002$) scores.

These results demonstrated clinically significant improvements consistent with or better than previously reported behavioral therapy intervention outcomes in similarly aged participants. Overall, families played an average of 18 90-second game sessions over the four weeks, with an average of three 90-second gameplay sessions per day of use and average of six days of use over the four weeks. These sessions generated almost 1,000 videos (24 hours in total) used to generate 300,000+ frames labeled with a host of app and sensor data such as choice of game deck, number of correct guesses, etc., providing strong evidence for the feasibility of using GW to generate a rich behavioral database for training pediatric neurodevelopmental AI models.

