10.5 Stratification, Subgroup Analysis and Pooled Analysis

Following consent, those subjects meeting all entry criteria will be randomized in a 1:1 ratio. Random blocks of size 2 or 4 will be utilized.

[Efficacy Endpoint Analysis](#)

1. Objective

To compare the change in outcome measure scores between treatment and treatment as usual groups in a clinical trial.

2. Study Design

Participants: Treatment and Treatment as Usual groups

Outcome Measure: Continuous outcome measure scores measured at baseline and follow-up on VABS-3 Socialization Subscale and Parent Stress Scale.

3. Statistical Hypotheses

Null Hypothesis (H_0): There is no difference in the change in outcome measure scores between treatment and control groups.

Alternative Hypothesis (H_1): There is a significant difference in the change in outcome measure scores between treatment and control groups, whereby treatment participants scores demonstrate improvement.

4. Variables

Independent Variable: Group (Treatment vs. Control)

Dependent Variable: Change in outcome measure scores (Post-test score - Pre-test score)

5. Statistical Method

Primary Analysis: Independent samples t-tests will be used to compare the mean change in outcome measure scores between treatment and control groups.

6. Assumptions

Normality: The change in outcome measure scores in each group should be approximately normally distributed. If not, consider transformations or non-parametric tests.

Equal Variances: The variances of change scores in the treatment and control groups should be approximately equal. If violated (checked using Levene's test), use Welch's t-test or report results with caution.

7. Statistical Software

Analysis Tool: SPSS, R, or any other statistical software capable of performing independent samples t-tests.

Descriptive analyses

Descriptive statistics (proportions for categorical variables, means, medians, standard deviations, and interquartile ranges for continuous variables) will be reported for all key patient variables, including baseline and demographic characteristics, use of medications, compliance, and study completion status. Data that are missing on key patient characteristics and the outcome will be fully described, including any patterns of missingness (i.e., any relationships between missingness of a variable and patient characteristics).

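### Section 10.2 prints 90% power for 3.1 points without an SD; it needs a change-score SD of about 9.05, while the feasibility result at face value implies about 13.9 and about 56% power

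*Combined protocol and SAP*

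**What the plan says.** Section 10.2 sets the target at 360 completers, 180 per arm, "estimated for 90% power and 2-sided significance of .05 to detect minimal differences in VABS-III Socialization Standard Score of 3.1 points". It describes this as consistent with a feasibility study by the same lab and makes 360 participants with completed endpoints the rule for closing the study. It prints no SD for the change score.

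Section 10.5 fixes the test: "Independent samples t-tests will be used to compare the mean change in outcome measure scores between treatment and control groups". Section 10.1 fixes the error rate: "Hypothesis tests will be two sided and conducted at an overall alpha = 0.05 level of significance".

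Section 3.2 describes the only GuessWhat feasibility study in the document: "We examined the therapeutic feasibility of GuessWhat in 72 children". This was a single group followed for four weeks. Its Vineland result is given as "Vineland Adaptive Behavior Scales-II (VABS-II) socialization standard (5.27, $p=0.002$) scores". The SD, the test, and the number of children with both assessments are not given.

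The Synopsis gives a wider target than 10.2: "a minimum of 360 to a maximum 900 completed participants (n=180 - 450 in each of 2 arms) evaluable".

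**The concern.** A power figure for a two-sample t-test rests on four inputs: difference, sample size, alpha and SD. Section 10.2 prints three and leaves out the one that cannot be chosen. The only SD printed anywhere is the v-scale norm of 3 in section 9.1, which is on a different metric from the standard score used for power.

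This goes beyond an omission. Section 10.2 points to the lab's own feasibility work as support, and the one such result shown, read in the obvious way, suggests a change-score SD about 1.5 times what the 90% needs (13.9 / 9.05 = 1.54). If that reading is right, closing at 360 completers gives little better than an even chance of detecting the difference that the plan calls minimal. A non-significant result would then be read as evidence against a 3.1-point effect from a trial with 90% power, when the design could not bear that reading.

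**Working it through.** **Inputs.** Difference 3.1, 180 per arm, 90% power, two-sided 0.05 (sections 10.1 and 10.2); independent-samples t-test on change (10.5); pilot of 72 children, change 5.27, p=0.002 (3.2); up to 450 per arm (Synopsis).

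**1. The plan's own figure.** The 90% cannot be reproduced, because no SD is given. It can be inverted for the SD it needs:

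SD = 3.1 / [(1.960 + 1.282) × √(2/180)] = 3.1 / (3.242 × 0.1054) = 9.07

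The noncentral t gives 9.05. The standardised difference is 0.34.

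**2. The SD implied by section 3.2**, assuming a two-sided paired t-test on all 72:

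- t(0.999, 71 df) = 3.209
- SE = 5.27 / 3.209 = 1.642
- SD = 1.642 × √72 = 13.93

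A p-value that rounds to 0.002 lies between 0.0015 and 0.0025, which gives SD 13.54 to 14.26.

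**3. Power for 3.1 points at 180 per arm with that SD.**

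SE of the difference = 13.93 × √(2/180) = 1.468; 3.1 / 1.468 = 2.111; power = Φ(2.111 − 1.960) = 56.0% (noncentral t 55.8%).

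Over the rounding range of p, power is 54% to 58%.

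**4. Difference detectable with 90% power at 180 per arm.** 3.242 × 1.468 = 4.76 (noncentral t 4.77), so about 4.8 points; 4.6 to 4.9 over the rounding range.

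**5. Sensitivity to the number with paired scores**, holding 5.27 and p=0.002:

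| Paired scores | Implied SD | Power, 3.1 points, 180 per arm |
|---|---|---|
| 72 | 13.9 | 56% |
| 60 | 12.6 | 64% |
| 50 | 11.4 | 73% |
| 40 | 10.1 | 83% |
| 33 | 9.0 | 90% |

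**6. Other sensitivities, with all 72 paired.**

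- Sampling error: the 95% interval for the SD is 12.0 to 16.7. At the lower limit, power is about 69%.
- Reading p as one-sided gives SD 15.0 and power 50%. A z-test gives SD 14.5 and power 53%.
- If 13.93 held only in the treated arm and the control SD were 10, 7, 5 or 0 (assumed values), power would be 68%, 76%, 80% or 85%.

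**7. Top of the Synopsis range.** At 450 per arm and SD 13.93: SE = 13.93 × √(2/450) = 0.929; 3.1 / 0.929 = 3.338; power = Φ(3.338 − 1.960) = about 92%.

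**The case against.** A reader might infer that the feasibility result contradicts the 90%, or that the true power is 56%. The documents do not support either statement. Section 3.2 says that 72 children were asked to play. It does not say how many had both Vineland assessments, which test was used, or what the SD was. The missing input therefore leaves the power undetermined, and some possible values agree with the printed figure.

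Incomplete pairing is not far-fetched in this programme. Section 10.2 itself plans for 36% retention. If that rate is applied to the pilot, purely as an assumption, 0.36 × 72 gives about 26 paired children, SD 7.8 and power about 96%.

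The link between the sections is also loose. Section 10.2 claims consistency with a feasibility study but does not say that its SD came from there. The only Vineland change in 3.2 is 5.27, not 3.1, so 10.2 may rest on figures that are not shown. The pilot used VABS-II in one uncontrolled group, whereas the trial uses VABS-3 in two arms.

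All of this stands, and it limits the finding to a conditional one. It does not remove it. The plain reading of 3.2 is that the result describes the group of 72. The 90% returns only if fewer than half of them contributed paired scores, or if the change SD in this trial is well below the pilot's. Neither is stated, and the sponsor holds the data that would settle the first.

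**Conclusion.** The 90% power in section 10.2 cannot be verified as printed, and the only supporting evidence shown does not support it at face value. It needs a change-score SD of about 9.05. The pilot read as a two-sided paired t-test on all 72 children implies about 13.9, hence about 56% power for 3.1 points (54% to 58%) and 90% power only for about 4.8 points.

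The conclusion rests on three assumptions: all 72 had paired scores, the SD carries over from VABS-II to VABS-3, and it applies to both arms. The first matters most, since power rises to 64%, 73% and 83% with 60, 50 and 40 paired children and reaches 90% at about 33. The point is an unsupported power claim attached to a close-out rule. It is not a demonstrated arithmetic error, and 56% should not be quoted without its conditions.

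**What to change.** From the pilot data that the lab holds, compute the SD of change in the Socialization standard score and the number of children with paired scores. Print both in section 10.2 with their source. Then restate, for 180 completers per arm, either the power for 3.1 points or the difference detectable with 90% power.

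If the SD proves to be near 13.9, replace the present claim with about 56% power for 3.1 points and 90% power for about 4.8 points. If it proves to be near 9, the claim can stand once the SD and the number analysed are shown. The back-calculated 13.9 should not itself be printed as the pilot SD.

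Also reconcile the close-out at 360 completers with the Synopsis range of 180 to 450 per arm, and say what decides where in that range the trial stops.

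Cost: one calculation on existing data and a revision of 10.2. The stated power may become less favourable. Restating it needs no extra participants. Raising the target would be a separate design decision: at 36% retention of enrolled families, 900 completers would need 900 / 0.36 = 2,500 enrolled, above the stated maximum of 2,000.
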